#### 3.2 Exclusion Criteria

The exclusion criteria are established to exclude the following situations: 1) patients who might be at risk from participation, 2) eligible patients who do not want to be enrolled and 3) those who are unlikely to comply with the study guidelines. Note that patients who have a medical need for aspirin will not be excluded from participation in this study.

A woman who is pregnant or is breastfeeding may not participate in this research. A pregnancy test will be performed for any woman who has neither been amenorrheic for the previous 12 months nor surgically sterilized and who is sexually active and not using an acceptable means of birth control (condom, diaphragm and spermicide, oral or injected contraceptives, IUD) and who wishes to participate in this study. It is the responsibility of the patient to use acceptable methods of birth control (condom, diaphragm and spermicide, oral or injected contraceptives, IUD, surgical sterilization, and abstinence). If the patient is a woman who can bear children and suspects pregnancy during the time she receives treatment in this study, she should notify the study staff immediately. If she is pregnant, her study medication will be discontinued.

The exclusion criteria are:

- 1. Women must not be pregnant, breast feeding, or plan to be pregnant during the course of the study.
- 2. The presence of ongoing bleeding.
- 3. The presence of a known bleeding disorder (e.g., hemophilia or von Willebrand's disease)
- 4. Recent bleeding episode requiring transfusion within 12 weeks of entry.
- 5. The presence of acute ulcer disease. Acute ulcer disease is defined as a new diagnosis of peptic disease including esophagitis, gastritis, or ulcer or the initiation of treatment for acute ulcer disease with proton pump inhibitors, H2 blockers or therapy for Helicobacter pylori within three months prior to obtaining consent.
- 6. Known allergy or adverse reaction to Aggrenox or any of its study components (dipyridamole and aspirin).
- 7. Required use of warfarin, dipyridamole, non-steroidal antiinflammatory drugs or other antiplatelet agents other than aspirin.

- 8. Current uncontrolled hypertension with systolic blood pressure in excess of 200 mm Hg or diastolic blood pressure in excess of 115 mm Hg.
- 9. Baseline platelet count less than 75,000/mm^3.
- 10. Known advanced liver disease with decompensated cirrhosis, jaundice, ascites or bleeding varices.
- 11. Current problem with substance abuse.
- 12. Concurrent participation in another medical intervention trial.
- 13. Anticipated non-compliance with medical care based on physician judgment.
- 14. Patient refusal.

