# 3. ENROLLMENT, RANDOMIZATION, AND BLINDING

The study population will be drawn from patients with end-stage renal disease or chronic renal failure approaching the need for dialysis who receive a new arteriovenous access at one of the participating Clinical Centers. Since the practice patterns at each participating unit will vary, the senior investigator and study coordinator at each unit will need to develop a strategy appropriate for their own unit to identify and recruit all eligible subjects. The potential subject should be approached prior to access surgery to provide information about the study and determine eligibility for enrollment. Subjects will be given time to read the informed consent documents and ask questions about their participation in the study. If the patient meets eligibility criteria and agrees to participate s(he) will be asked to sign the informed consent document and baseline enrollment data will then be obtained. It is preferred that this visit occur prior to placement of the new graft; however, enrollment will be permitted up to two calendar days following access surgery. Patient enrollment and baseline data collection will be take place within 45 days prior to randomization. If the surgery gets rescheduled for a date more than 45 days after the initial enrollment then new baseline data will need to be obtained. If more than 90 days elapses between the time of signing the original informed consent and the access surgery, the subject will be re-apprised about the study and a new informed consent document as well as new baseline data will be obtained.

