# 3.3 Randomization

Subjects who have been enrolled in the study will be randomized within 2 days after successful placement of a new arteriovenous graft. Administration of the study drug should begin immediately following randomization. The optimal time for randomization and initiation of study medication would be in the postoperative recovery room after verification that a graft was placed. If the surgeon reports that the graft thrombosed in the operating room or in the recovery room, the patient should not be randomized. Subjects will be randomized to either Aggrenox or matched placebo in a ratio of 1:1. Randomization will be stratified by Clinical Center and by access (lower arm or at another site). A random permuted block design will be used to assure approximate balance over time. Randomization will be performed via the internet using a Web browser following verification of eligibility by the Data Coordinating Center. Stratification based on Clinical Center is designed to minimize the influence that differences in baseline risk between different centers might have on study outcome. While one source of variability is likely to be surgical expertise (62), the number of access procedures done by each surgeon is expected to be so small that stratification by surgeon is not likely to be feasible. The location of the graft in the upper or lower arm has been shown to strongly influence graft survival in some studies and thus randomization will also be stratified by this variable (55, 63, 64). Since leg grafts and other heroic graft sites (e.g., necklace graft) have a high flow rate, they will be categorized as an upper arm graft for the purpose of stratification (63).

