#### 4. STUDY TREATMENT PLAN

#### 4.1 Study Visits

Subjects should be seen prior to creation of the access for enrollment and collection of baseline data. The subject will be evaluated again within 2 days after creation of the new access to confirm that an eligible graft had been placed and is patent. If the access is patent, the subject will be randomized into the study and the first months supply of study medication will be provided. The patient will be asked to take their first dose of medication at that time.

Following randomization, subjects will be seen at monthly intervals throughout the duration of the study. It is anticipated that most subjects will be undergoing hemodialysis and will be seen at the time of a scheduled hemodialysis session. For subjects on hemodialysis, each monthly visit will include a measurement of access flow rate along with collection of study data including an assessment of access related procedures, complications, hospitalizations and compliance with the study medication (Section 6.2 below). For those subjects not yet on hemodialysis a monthly visit will need to be arranged to assess access patency and collect study data.

The subject will remain on study medication until the primary endpoint is reached, at which point the medication will be terminated. The monthly visit schedule will continue until the first regularly scheduled monthly visit following the primary endpoint. At closeout, the functional status of all accesses and survival of all patients that had been enrolled in the study will be determined and if total site failure or death has occurred, the time of these events will be recorded. Each monthly visit will include an assessment of potential adverse events.

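### Section 3.2 clears contraceptive users for the pregnancy exclusion on history alone, so an unrecognized pregnancy can reach the first dose

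*Protocol*

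**What the plan says.** Exclusion 1 in Section 3.2 is unconditional: "Women must not be pregnant, breast feeding, or plan to be pregnant during the course of the study". The testing rule in the same section is conditional. It applies to a woman who has not been amenorrheic for 12 months and who also is not "surgically sterilized and who is sexually active and not using an acceptable means of birth control"; the last two conditions are joined to the first two by the word *and*. Contraception is left to the patient. If she "suspects pregnancy during the time she receives treatment in this study, she should notify the study staff immediately", and study medication stops if she proves to be pregnant.

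On timing, Section 3 states: "Patient enrollment and baseline data collection will be take place within 45 days prior to randomization". It prefers enrollment before the graft is placed, but "enrollment will be permitted up to two calendar days following access surgery". Section 3.3 has randomization performed "following verification of eligibility by the Data Coordinating Center", and then "Administration of the study drug should begin immediately following randomization". Section 4.1 describes the visit after surgery as one at which the subject is "evaluated again within 2 days after creation of the new access to confirm that an eligible graft had been placed and is patent". The baseline list in Section 6.1 names a blood count and albumin as laboratory items and does not name a pregnancy test.

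**The concern.** An eligibility rule should be able to detect the condition it excludes. Here the exclusion covers all pregnant women, but the test meant to find them depends on what the woman reports about sexual activity and contraception. A sexually active woman using a listed method can give an entirely accurate history and still be pregnant without knowing it. The rule does not test her.

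At stake is avoidable exposure of a pregnancy to study drug in a trial that chose to exclude pregnancy. The later safeguards, self-report and stopping the drug, act once she suspects pregnancy on treatment, which is after exposure has begun.

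**Working it through.** No power or error-rate calculation applies. The check has three parts.

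**1. Who is tested.** Take a woman who is neither sterilized nor 12 months amenorrheic. Two yes/no conditions remain, giving 2 × 2 = 4 combinations:

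- sexually active, no acceptable method: test required;
- sexually active, acceptable method: no test required;
- not sexually active, no acceptable method: no test required;
- not sexually active, acceptable method: no test required.

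One of the four combinations is tested. The second matters most, because risk remains even when the history is true. In the last two, risk arises only if the report is wrong or has become outdated.

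**2. Whether another provision closes the gap.**

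- Section 3.3: the Data Coordinating Center verifies eligibility before randomization. This makes the test implicitly a pre-randomization step, but verification cannot reveal a pregnancy in a woman who was not tested.
- Section 4.1: the purpose given for the post-surgery visit is graft eligibility and patency. No pregnancy check is mentioned.
- Section 6.1: none of the 16 baseline items is a pregnancy test.
- Sections 6.2.2 and 6.2.3: neither the monthly visit list nor the five adverse event questions include a pregnancy test or question.
- Section 3.2: self-report and drug stop apply during treatment.

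None of these provisions requires a test for the three untested combinations.

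**3. How old a result may be.** Section 3.2 attaches no timing to the test. By contrast, exclusions 4 and 5 state their own periods (12 weeks and three months). If the test is treated as baseline data:

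- Section 3 limit: 45 days before randomization, 45/7 = 6.4 weeks.
- Section 6.1 limit: 45 days before graft creation, plus up to 2 days to randomization, 45 + 2 = 47 days, 47/7 = 6.7 weeks. Section 3 is tighter, so 45 days governs.
- Woman enrolled after surgery: as little as 0 days.

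The range is therefore 0 to 45 days. Section 3 requires new baseline data if surgery moves beyond 45 days after enrollment. Whether that includes a repeat pregnancy test is not stated.

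**The case against.** The strongest defense is that this is a deliberate, risk-tiered rule. It targets the women at highest risk and sits beside a flat exclusion, a bar on planned pregnancy, a contraception duty, a reporting duty and a drug-stop rule. These parts do not contradict one another. The population is described as aging, Section 1.5 names no fetal risk, and nothing in the protocol allows the harm to be quantified. All of this stands, and it limits the weight of the point. It does not remove the point: followed exactly, the rule can still admit a woman whom exclusion 1 bars.

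A reader might infer that the test has no time limit at all. The documents do not support that. Section 6.1 says the baseline evaluation serves to confirm the eligibility criteria and asks for data as near to graft creation as possible, and Section 3 sets the 45-day limit. A test done for eligibility falls naturally under those provisions, though only by inference. What remains is that the test has no window of its own and that 45 days is long for this purpose.

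A reader might also infer that the post-surgery visit is restricted to the graft, or that test results go unrecorded. Section 4.1 states a purpose without excluding other checks, and the Section 6.1 list is introduced as what the data should include. The silence shows that no check is required, not that none is made. Sites may test more widely in practice.

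Finally, a shorter window has a real cost. Baseline may precede surgery by weeks, so a test near surgery may need a separate sample. The fix has to allow for this.

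**Conclusion.** The point holds as a minor safety improvement. For women able to conceive who report contraception, and to a lesser degree those reporting no sexual activity, exclusion 1 is applied on history alone, and an unrecognized pregnancy can reach the first dose. For women who are tested, a negative result may be up to 45 days (6.4 weeks) old at randomization, assuming the general baseline window covers the test.

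The number affected cannot be derived. The protocol gives neither the number of women able to conceive nor a contraceptive failure rate, so no count of exposed pregnancies is claimed; it is probably small. A reader might take this as a threat to the trial's results. It is not: sample size, power, error rate, estimand and primary analysis are untouched.

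**What to change.** In Section 3.2, replace the conditional rule with this: every woman who is neither surgically sterilized nor amenorrheic for the previous 12 months must have a negative pregnancy test before randomization, whatever she reports about contraception or sexual activity. The test should be taken as close to surgery as practical, for example with the pre-operative sample, or as a rapid test if she is enrolled after surgery. Add the result and its date to the Section 6.1 baseline data, so that the eligibility verification in Section 3.3 has a result to check.

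The cost is one revised sentence, one recorded item and a few additional uses of a test the protocol already requires for some women. A separate sample may be needed, because Section 6.1 accepts existing laboratory values up to 45 days old and Section 6.2.5 lets the stored research sample be drawn at a later visit. An occasional false positive would have to be repeated within the 2-day randomization window, which is tightest for women enrolled after surgery.

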
The inclusion criteria are:

- 1. Age equal or greater than that at which consent can be obtained without parental involvement (18-21 years depending on state regulations).
- 2. Life expectancy of at least six months.
- 3. Chronic renal failure with anticipated start of hemodialysis within six months of enrollment, or current dialysis-dependence.
- 4. A new or planned AV graft placed in any location for the purpose of hemodialysis. (Any type of graft material and any configuration of the access is acceptable).
- 5. The patient is expected to stay at a participating dialysis facility for at least 6 months.
- 6. The patient's physician(s) will allow the patient to participate.
- 7. Ability to give informed consent.

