#### 4.3.1 Bleeding

Aggrenox has a small dose of aspirin that will increase the risk of bleeding. Bleeding will be classified as either minor, intermediate, major, life-threatening or fatal. Minor bleeding events are episodes of bleeding that did not require an event-related visit or follow-up or discontinuation of the study drug. Intermediate bleeding is a bleeding event that does not meet criteria for a major bleed but required an event-related visit with a health care provider or temporary discontinuation of study medication. Examples of minor or intermediate bleeds might include superficial cuts, abrasions, bruises, nose bleeds, or vaginal bleeding events. The presence of a hemoccult positive stool alone that leads to non-emergent evaluation such as a colonoscopy and is not associated with a 2 g/dl drop in hemoglobin or the need for a transfusion will be considered an intermediate bleeding event. Major bleeding is defined as a confirmed retroperitoneal, intra-articular, intraocular, or intracranial bleed or any bleed that leads to a drop in hemoglobin by 2 g/dl and requires hospitalization or the need for a transfusion, causes a symptomatic intracranial hemorrhage, or requires a transfusion of more than 4 units of packed RBCs or whole blood. Fatal bleeding is any bleed that causes or precipitates death.

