Management of bleeding should be handled as for a patient on aspirin. For minor episodes of bleeding (e.g., superficial abrasion or nose bleed) conservative measures to control the bleeding should suffice without the requirement for discontinuing study medication. Short-term discontinuation of study medication during an intermediate bleeding episode with re-institution when stable is allowed. If the patient has a major or life-threatening bleed the study medication will be discontinued and not restarted. In the event of a cerebrovascular accident occurring during active treatment, computed tomography or magnetic resonance imaging should be performed to exclude intracerebral hemorrhage. For intermediate bleeds the decision to stop study drug will be made by the physician(s) caring for the patient. If the patient has a major or life-threatening bleed the study medication will be discontinued and not restarted unless the bleed is caused by either a surgical procedure or trauma and it is established 1) that the cause of bleeding has been eradicated, and 2) that the bleeding event does not reflect an underlying bleeding tendency or predispose to recurrent bleeding. Study drug resumption in this situation must be approved by the physician(s) caring for the patient. Bleeding events will be actively monitored and recorded by the study coordinator throughout the patient's participation on the study. An expert panel will review all major and life-threatening bleeds as well as a randomly selected subset of other bleeding events.

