#### 4.3.6 Discontinuation of Therapy

Adverse events leading to cessation of study drug, but not termination from the study will include:

- 1. Development of an intestinal ulcer or gastrointestinal bleeding while on the study medication.
- 2. An adverse event attributed to the study medication such as intolerable persistent headache, diarrhea or dizziness without other etiology that does not respond to medical management.
- 3. A bleeding disorder (e.g., a major or life-threatening bleed) that contraindicates the continued use of Aggrenox.
- 4. A new medical requirement for long-term anticoagulation or antiplatelet therapy other than aspirin.
- 5. A new medical requirement for using Aggrenox or dipyridamole.

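### Exclusion 4 bars a recent bleed only if it required transfusion, so a resolved, untransfused intracranial or retroperitoneal bleed in the 12 weeks before entry meets no numbered exclusion

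*Protocol*

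**What the plan says.** Section 3.2 (Exclusion Criteria) opens by naming the groups it is meant to keep out. The first is "patients who might be at risk from participation". Among the 14 numbered exclusions, those that bear on bleeding are:

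- exclusion 2: bleeding that is still going on;
- exclusion 3: "The presence of a known bleeding disorder", with hemophilia and von Willebrand's disease as its examples;
- exclusion 4: "Recent bleeding episode requiring transfusion within 12 weeks of entry";
- exclusion 5: acute ulcer disease, meaning peptic disease newly diagnosed or newly treated in the previous three months;
- exclusion 9: a platelet count below 75,000/mm³;
- exclusion 10: decompensated liver disease, including bleeding varices.

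Section 3.1, inclusion 6, requires that the patient's "physician(s) will allow the patient to participate". Section 6.1 says that one aim of the baseline evaluation is to make sure patients are not at risk of complications of therapy. Its history items include stroke, TIA and coagulopathy.

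For bleeds on study, section 4.3.1 says: "Major bleeding is defined as a confirmed retroperitoneal, intra-articular, intraocular, or intracranial bleed or any bleed that leads to a drop in hemoglobin" of 2 g/dl with further conditions. Bleeds at the four named sites are thus major by site alone. After a major bleed the drug is "discontinued and not restarted unless the bleed is caused by either a surgical procedure or trauma", and then only if two further conditions are met and the treating physician approves.

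**The concern.** Need for transfusion measures blood loss. It is a poor marker of danger at sites where a small bleed can do serious harm, and section 4.3.1 reflects this by grading intracranial and retroperitoneal bleeds as major without asking about transfusion. Exclusion 4 asks only about transfusion. As written, a patient with such a bleed shortly before graft surgery can be randomized if the physician agrees, and would start an aspirin-containing drug within two days of surgery.

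Section 6.2.6 names bleeding as the main risk expected from the study drug. Section 1.5 expects serious bleeds to rise 2- to 4-fold over control, attributes the rise to aspirin, and notes that aspirin prolongs bleeding time more in end-stage renal disease. What is at stake is the safety of a few individual patients. The treatment comparison, its power and its type I error are not affected.

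**Working it through.** No design figure depends on this point, so the main check is a reading of the criteria.

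**Step 1. Test case.** Take a patient with a confirmed intracranial or retroperitoneal bleed six weeks before entry, now resolved, that did not require transfusion.

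| Criterion | Does it exclude because of the bleed? |
|---|---|
| Exclusion 2, current bleeding | No, the bleed has resolved |
| Exclusion 3, bleeding disorder | Not on its natural reading (step 2) |
| Exclusion 4, transfused bleed | No, transfusion was not required |
| Exclusion 5, acute ulcer disease | No, different site |
| Exclusions 7 and 8, required drugs and uncontrolled blood pressure | Only if present for another reason |
| Exclusions 9 and 10, platelets and liver disease | Only if present for another reason |
| Exclusions 1 and 11–14 | Unrelated |
| Inclusion 6, physician permission | Discretion; bleeding is not mentioned |

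**Step 2. Could exclusion 3 cover it?** Section 4.3.6, item 3, lists among reasons to stop the drug "A bleeding disorder (e.g., a major or life-threatening bleed) that contraindicates the continued use of Aggrenox". Carried back to exclusion 3, that usage would make a recent major bleed a bleeding disorder. Two things speak against this. Exclusion 3 gives its own examples, and both are inherited coagulation defects. Also, under section 4.3.1 major bleeding includes "any bleed that leads to a drop in hemoglobin by 2 g/dl and requires hospitalization or the need for a transfusion". A transfused bleed with that fall in hemoglobin would then be barred by exclusion 3 with no time limit, which leaves exclusion 4 and its 12-week window with little to do.

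**Step 3. Could the baseline review cover it?** Section 6.1 gives a purpose and a list of history items. It does not separate hemorrhagic from ischemic stroke, has no item for recent bleeding, and sets no eligibility rule. Under section 3.3 the Data Coordinating Center verifies eligibility before randomization, but the numbered criteria give it nothing to check on these bleeds.

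**Step 4. Do untransfused intracranial bleeds occur?** The stroke-prevention trial tabulated in section 1.5 defined severe bleeding as bleeding that required transfusion. Assume that the severe-or-fatal row uses this definition and includes intracranial bleeds. The least number of intracranial bleeds that were neither transfused nor fatal is then max(0, intracranial − severe or fatal):

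- placebo: 14 − 7 = 7
- aspirin: 16 − 20 < 0, so 0
- dipyridamole: 11 − 6 = 5
- combination: 16 − 27 < 0, so 0

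The total is at least 12 of 14 + 16 + 11 + 16 = 57, or 21%. A transfusion test can therefore miss intracranial bleeds. This says nothing about how often that happens in dialysis patients.

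**Step 5. Order of size, as illustration only.** Section 1.5 quotes a yearly serious-hemorrhage rate of 1–1.5% in hemodialysis patients on placebo. It is a personal communication that does not define serious. Assume that it applies to the 12 weeks before entry:

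- 1056 × 0.010 × 12/52 = 2.4
- 1056 × 0.015 × 12/52 = 3.7

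These are serious bleeds at all sites. Transfused, ongoing, peptic and variceal bleeds are already excluded, which lowers the number in the gap. If serious meant transfused, the rate would not count the bleeds at issue at all. The range is not a bound in either direction.

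**The case against.** The best answer is that this is a choice of threshold. Transfusion is how the stroke-prevention trial defined a severe bleed, section 1.5 leans on that trial, and excluding recent bleeds at that level is coherent. Entry rules need not mirror stopping rules. There are also layers of protection: a physician must agree, the baseline history would probably bring a recent intracranial bleed to light, and the wording of section 4.3.6 gives a site some ground to refuse. Nor does the reviewed evidence show an excess of intracranial bleeding. Cerebral bleeds were 12 against 12 in the hypertension trial, and intracranial bleeds were 1.0% against 0.8% in the stroke-prevention trial (combination against placebo).

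Much of this stands. The protections make enrolment of such a patient less likely, and frequency and harm in this population are not shown. What remains is that no protection is an eligibility rule, so the outcome depends on the site. The reassuring bleeding rates are not presented as coming from patients with a recent bleed at these sites.

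Three stronger readings are tempting, and the protocol supports none of them.

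- *Sections 3.2 and 4.3.1 contradict each other.* They do not. They serve different purposes, and 4.3.1 shows only how the protocol itself grades these bleeds.
- *Recent major bleeds in general are let in.* They are not. Transfused, ongoing, newly diagnosed peptic and variceal bleeds are all covered.
- *Every recent bleed with a 2 g/dl fall in hemoglobin and hospital admission should also be barred.* That threshold is debatable. It would catch resolved surgical or access bleeds, after which section 4.3.1 allows the drug to be resumed on study.

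**Conclusion.** The gap is real and narrow: a resolved intracranial or retroperitoneal bleed within 12 weeks of entry that did not require transfusion meets no numbered exclusion. This rests on reading exclusion 3 by its own examples. If sites carried the section 4.3.6 usage back to entry, most such patients would be kept out, but the text would then be open to two readings, which is also a reason to clarify it.

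Severity is low, an improvement the sponsor could make. Frequency cannot be bounded from the protocol, and the figures in steps 4 and 5 only illustrate. Power, alpha and the primary analysis are untouched.

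**What to change.** Reword exclusion 4 along these lines: *Bleeding episode requiring transfusion, or any confirmed intracranial or retroperitoneal bleed whether or not transfused, within 12 weeks of entry.* This only adds to the criterion, so no patient excluded today becomes eligible.

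Leave two matters to the sponsor. One is whether to add intraocular and intra-articular bleeds, which section 4.3.1 also grades as major by site. The other is whether to add untransfused bleeds with a 2 g/dl fall in hemoglobin and hospital admission. If the latter are added, the surgery and trauma exception of section 4.3.1 should come with them, so that entry is not stricter than the on-study rule.

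The cost is a one-line amendment to section 3.2 and the eligibility form, with the IRB approval that section 11.1 requires. Probably a very small number of otherwise eligible patients would be lost; the protocol gives no rate from which to bound that number.

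### Exclusion 5 counts recent ulcer disease back from consent, although dosing starts at randomisation, so events between the two are not clearly excluded

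*Protocol*

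**What the plan says.** Protocol Section 3.2, exclusion 5, opens by barring patients in whom acute ulcer disease is present, then defines the term. The definition has two limbs, joined by an or: a new diagnosis of peptic disease, and the start of treatment with acid-suppressing or Helicobacter drugs. It closes with the time phrase "within three months prior to obtaining consent".

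The timeline is set in Sections 3 and 3.3:

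- At the enrolment visit the patient is asked to "sign the informed consent document and baseline enrollment data will then be obtained".
- "Patient enrollment and baseline data collection will be take place within 45 days prior to randomization".
- Enrolment before surgery is preferred, but "enrollment will be permitted up to two calendar days following access surgery".
- If surgery moves to a date "more than 45 days after the initial enrollment then new baseline data will need to be obtained". No new consent is required at that point.
- "If more than 90 days elapses between the time of signing the original informed consent and the access surgery", both consent and baseline data are renewed.
- Enrolled subjects "will be randomized within 2 days after successful placement of a new arteriovenous graft".
- "Administration of the study drug should begin immediately following randomization".

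Section 3.3 has the Data Coordinating Center verify eligibility before assignment. Section 4.1 describes the post-operative evaluation as a check that an eligible graft is in place and patent. Section 6.1 asks for baseline data as near to graft creation as can be managed, with 45 days as the ceiling.

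**The concern.** An exclusion for recent ulcer disease protects the patient at the moment exposure begins, which here is randomisation and first dose. A window that closes at consent can leave the most recent and most relevant period outside the definition while still excluding older disease.

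The drug makes this worth attention. Section 6.2.6 names bleeding as the main expected risk. The large hypertension trial of aspirin summarised in Section 1.5 had 72 non-fatal major gastrointestinal bleeds on aspirin against 34 on placebo, and the same section expects a higher background rate of serious bleeding in haemodialysis patients. Section 4.3.6 stops study drug for an intestinal ulcer or gastrointestinal bleed, but only one that develops on treatment. A peptic event between consent and first dose could therefore fall between the entry rule and the stopping rule.

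**Working it through.** The plan gives no figure to reproduce; the check is day arithmetic on the timeline.

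**Inputs**

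- L, the look-back: three months, taken as 91 days (assumption).
- g, the days from consent to randomisation:
  - at most 2 if the patient is enrolled after surgery (Sections 3 and 3.3);
  - at most 45 in the ordinary case (Section 3; consent and baseline belong to the same enrolment step);
  - at most 90 + 2 = 92 if surgery is rescheduled and consent is not renewed (Sections 3 and 3.3).
- A 14-day gap is added as an illustration only.

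**Formulas**, with randomisation as day 0

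- The window as written runs from day −(g + L) to day −g.
- Share of the last L days before randomisation that is not covered = min(g, L) / L.
- Oldest event still excluded = g + L days before randomisation.

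| Gap g (days) | Uncovered share of last 91 days | Oldest event still excluded (days) |
|---|---|---|
| 2 (enrolled after surgery) | 2/91 = 2% | 2 + 91 = 93 |
| 14 (illustration) | 14/91 = 15% | 14 + 91 = 105 |
| 45 (ordinary limit) | 45/91 = 49% | 45 + 91 = 136 |
| 92 (rescheduled, consent unchanged) | 91/91 = 100% | 92 + 91 = 183 |

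**What the shares apply to** depends on how the definition is parsed.

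1. *The time phrase governs both limbs.* The shares apply to new diagnoses and to treatment starts. At a 45-day gap, a diagnosis made 136 days before dosing is excluded, while one made a week before dosing does not meet the definition.
2. *The time phrase governs only the treatment limb.* A new diagnosis is excluded whenever made. The shares then apply only to treatment begun after consent for peptic disease already known.

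**Does other text re-date the criterion?** In the ordinary case the baseline medication list (Section 6.1) is taken when consent is signed, so it cannot show a drug started later. In the rescheduled case the list is retaken and could show such a drug, but the consent date in exclusion 5 does not move. Exclusion 2 requires ongoing bleeding and exclusion 4 a transfused bleed, so neither reaches a non-bleeding ulcer. No section names an ulcer recheck between consent and first dose.

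**The case against.** The strongest reply is that the protocol, read sensibly, already protects these patients. Exclusion 5 opens in the present tense, which an investigator may apply on the day of randomisation. The time phrase directly follows the treatment limb, and the diagnosis limb carries its own word for recency, so the narrower parsing is reasonable. Section 3.2 says the exclusions are meant to remove patients whom participation might put at risk. Section 6.1 makes confirming the inclusion and exclusion criteria the first purpose of the baseline evaluation, and that evaluation is repeated when surgery slips past 45 days. The patient's physician must agree to participation, and the Data Coordinating Center verifies eligibility before assignment. Dating history criteria from consent is also common, because the history is taken then.

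Much of this stands, and it rules out some stronger readings. A reader might infer that exclusion 5 plainly lets a patient with a newly found ulcer start the drug. The text does not support that without qualification, since it fails on the narrower parsing and on the present-tense opening. A reader might take 45 days as the usual wait; Section 6.1 shows that it is a ceiling. Nor can one say that sites make no recheck, because the content of the web form and of the verification is not shown.

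What does not stand is that these safeguards settle the matter. The opening words are followed at once by a definition with a different anchor. Verification against the written criterion inherits that anchor. The monthly questions on bleeding and stomach symptoms (Section 6.2.3) come only after dosing has begun.

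**Conclusion.** The point holds as a minor safety gap in the wording of exclusion 5: the rule is stated, but its anchor is consent rather than the start of exposure. Its size is calendar coverage only, not risk. On the broader parsing the uncovered stretch before first dose is at most 2 days for patients enrolled after surgery, up to 45 days ordinarily, and up to about 92 days when surgery is rescheduled. On the narrower parsing the same intervals apply to a smaller class of events.

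This rests on taking three months as 91 days and on consent being signed at the enrolment step. The protocol gives neither a rate of peptic events between consent and dosing nor a distribution of the gap, so no number of patients can be stated. A reader might be tempted to carry the point over to the trial's inference; nothing in the document supports an effect on type I error, power or the treatment comparison. The later cut-off for older ulcers (136 or 183 days) is extra caution and not a harm. It shows only that the ordering is the wrong way round.

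**What to change.** In exclusion 5, count the three months back from randomisation instead of from consent, and state that the window applies to both the diagnosis limb and the treatment limb. Have the coordinator re-confirm exclusions 2, 4 and 5 at the existing web randomisation step before an assignment is released; if the form already asks this, say so in the protocol. As a clarification only, name randomisation as the reference date in exclusion 4, where entry is undefined.

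The cost is a short wording change and three check fields, with no new visit or test. The downside is that a few patients who have consented and had surgery will be excluded late, though still before randomisation.

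With the window dated from randomisation, the uncovered interval falls to 0 days at every gap in the table.
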